### **2. Exclusion criteria**

Subjects excluded the following conditions: (1) contraindications for colonoscopy: such as cardiopulmonary insufficiency, etc. (2) Intolerance to PEG laxatives; (3) Pregnant women; (4) Mental disorders. Among them, the colonoscopy population without appendectomy was used as the control; 4) Use of antibiotics within half a year.

Control subjects excluded the following conditions: (1) presence of organic disease; Such as cardiopulmonary insufficiency, etc. (2) Pregnant women; (3) Mental disorders; 4) Use of antibiotics

[figure not shown]
within half a year.

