### **Iii. Study Design**

This study uses a parallel controlled monitoring clinical trial approach to investigate the short-term and long-term effects of PEG use on the gut microbiota of patients, including tracking analysis of the recovery and impairment of the gut microbiota, and comparing the recovery and impairment of the microbiota with those who did not undergo appendectomy to design corresponding microecological restoration probiotics. This study used bioinformatics methods to statistically analyze the data information of the samples.

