## **4. Selection of subjects**

### **1. Inclusion criteria**

The subjects were mainly recruited who met the following conditions: 1) Had undergone appendectomy or appendectomy for right-sided colon cancer; 2) were aged between 18 and 75 years old. 3) Prepare for colonoscopy; 4) Be in good health and have no history of major organ disease.

Control subjects were recruited to meet the following conditions: 1) age 18-75 years; 2) No appendectomy or right colon cancer appendectomy; 3) Good health, no history of major organ disease.

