## 5. Estimation of sample size

About 10 people were included in this study.

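### The eligibility lists for the appendectomy and control groups are not parallel, which puts the non-randomised recovery comparison (objective 2) at risk of confounding

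*Protocol*

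**What the plan says.** Objective 2 (Protocol, 2. Objectives of the study) asks whether the change in gut microbiota around colonoscopy differs between people without an appendix and the normal population. The Study Design section states: "This study uses a parallel controlled monitoring clinical trial approach".

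The groups are defined in section 4, Selection of subjects.

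- **Shared rules.** Both groups must be 18 to 75 years old. The appendectomy group must "Be in good health and have no history of major organ disease"; the control list has "Good health, no history of major organ disease". Both lists exclude pregnancy, mental disorders and antibiotics within the past half year.
- **Disease exclusion.** For the appendectomy group: "Subjects excluded the following conditions: (1) contraindications for colonoscopy: such as cardiopulmonary insufficiency, etc". For controls: "Control subjects excluded the following conditions: (1) presence of organic disease". Cardiopulmonary insufficiency is the example in both.
- **Appendectomy group only.** Its exclusion list continues "2) Intolerance to PEG laxatives; (3) Pregnant women; (4) Mental disorders", so PEG intolerance appears here and not for controls. Its inclusion list requires a forthcoming colonoscopy; the control inclusion list does not. It also admits people whose appendix was removed for right-sided colon cancer.
- **Source of controls.** A sentence placed inside the appendectomy group's exclusion list says that controls are colonoscopy patients who have not had an appendectomy.

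The sample size section reads "About 10 people were included in this study". It does not say whether this is a total or a number per group, and gives no split.

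**The concern.** With appendectomy status not randomised, the groups can be made comparable only by how people are selected or by adjustment. Adjustment has little room with about 10 people, so the eligibility rules carry most of the weight, and they differ by group. Followed as written, they can leave non-major organic disease and treated colon cancer in one group while removing organic disease from the other. They also leave the controls' exposure to PEG bowel preparation resting on one misplaced sentence. A difference in recovery could then reflect health status, bowel disease or preparation and be read as an effect of the missing appendix, which is what objective 2 sets out to learn.

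**Working it through.** **1. The two lists side by side** (Protocol section 4, inclusion and exclusion criteria)

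| Item | Appendectomy group | Controls |
|---|---|---|
| Age 18-75 | yes | yes |
| Good health, no major organ disease | yes | yes |
| Pregnancy, mental disorder, recent antibiotics | excluded | excluded |
| Disease exclusion | colonoscopy contraindication | organic disease |
| PEG intolerance | excluded | not listed |
| Planned colonoscopy | required | not in own list; implied by the misplaced sentence |
| Right-sided colon cancer surgery | admitted | barred |

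The first three rows agree; the last four do not.

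**2. What the disease rows let through.** The shared health criterion removes major organ disease from both groups. What remains is organic disease that is not major and does not contraindicate colonoscopy: a control with it is excluded, an appendectomy subject is not. The cancer row works in the same direction. It also conflicts with the appendectomy group's own health criterion, because a person with a history of colon cancer meets the first inclusion item and is hard to reconcile with the fourth.

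**3. Size of a possible bias.** The protocol gives neither the frequency of such disease nor its effect on the microbiota, so no value can be calculated. Suppose *k* of *n* appendectomy subjects have a condition barred among controls, and it shifts the outcome by an amount *d*. The spurious difference in group means is *k* x *d* / *n*. With *n* = 5 (about 10 taken as the total, split equally), each such person adds *d*/5. With *n* = 10 (about 10 taken as per group), each adds *d*/10.

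**4. Chance imbalance, a separate matter.** The sample size has no stated inputs, so there is no figure of the plan's own to reproduce. For illustration, with ages uniform on 18-75:

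- SD = 57/sqrt(12) = 16.45 years.
- 5 v 5: SD of the difference in mean age = 16.45 x sqrt(2/5) = 10.4 years; simulated chance of a gap above 10 years = 34%.
- 10 v 10: 16.45 x sqrt(2/10) = 7.4 years; chance = 18%.
- With an age SD of 10-12 years instead: 11-19% at 5 v 5 and 3-6% at 10 v 10.
- Sex, 50:50, 5 v 5: chance that the counts differ by two or more = 1 - 672/1024 = 34%.

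**5. Smallest attainable two-sided p of an exact rank test, total of 10**

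- Unpaired 5:5: 2/252 = 0.008. 7:3: 2/120 = 0.017. 8:2: 2/45 = 0.044. 9:1: 2/10 = 0.20.
- Five matched pairs, signed-rank: 2/2^5 = 2/32 = 0.0625, so 0.05 cannot be reached.
- Ten matched pairs (if about 10 is per group): 2/2^10 = 2/1024 = 0.002.

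Near-equal groups therefore help, but a paired rank test on five pairs would rule out significance at 0.05.

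**The case against.** The strongest reply is that the groups are more alike than the differing items suggest. A reader might infer that appendectomy subjects are screened only for colonoscopy contraindications. They are not: the good-health criterion and the pregnancy, mental-disorder and antibiotic rules bind both groups, and the antibiotic rule bears directly on a microbiota outcome. Both disease exclusions use the same example, so the authors may have meant much the same filter. That stands and narrows the gap to non-major organic disease and the cancer cases.

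A reader might also take the 34% figures as the size of the confounding. They are not: a randomised 5 v 5 trial would show the same chance imbalance, and they are the least favourable of the assumptions tried. Nor does an uneven split generally rule out significance. Among the splits of 10 shown, only 9:1 does so for an exact rank test, and the ANOVA with Tukey test named in section VIII has no such floor.

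Three further points hold. Objective 1 is a within-group comparison and is untouched. Objective 2 compares changes, so each person's baseline is available, although baseline values do not remove differences in how sicker people recover. The technical-route figure is not shown and may give the split, and covariate handling may sit in an analysis plan not at hand. None of this reconciles the two eligibility lists, which the protocol itself fixes.

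**Conclusion.** The point holds in a limited form. The lists differ on organic disease, PEG intolerance, planned colonoscopy and right-sided colon cancer, and the cancer item sits badly with its own group's health criterion. This exposes objective 2 to confounding by health status and bowel disease. A reader might go further and conclude that any group difference is confounded; the protocol supports a risk, not its presence, because who will actually be enrolled is unknown. The size cannot be calculated from the protocol. Under an assumed 5 v 5 split, each subject admitted by the looser rule has one fifth of the weight in that group's mean; if about 10 is per group, one tenth. The change is worth making because it reduces bias at almost no cost.

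**What to change.** - Reconcile the inclusion and exclusion criteria into one list for both groups, differing only in appendectomy status. Put planned colonoscopy with PEG preparation, the organic-disease item and the PEG-intolerance item in it in identical words, and move the sentence on the source of controls to the control definition.
- Resolve the conflict between admitting right-sided colon cancer cases and requiring no major organ disease. Which way is for the investigators to decide and state.
- Select controls from the same colonoscopy list, with a near-equal split and, where feasible, a similar age and sex distribution (frequency balance). State whether about 10 is the total or per group.
- Do not rely on a paired rank test if there are only about five pairs.
- Describe the comparison in objective 2 as observational and report its result as an association.

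Cost: protocol wording and slightly slower selection of controls. No additional participants or procedures are needed.

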## 5. Estimation of sample size

About 10 people were included in this study.

## Vi. Study Process

The technical route of this study is as follows:

## **Vii. Possible risks and Preventive measures**

The possible discomforts of this study include: psychological and sensory discomforts caused by fecal samples being mainly taken from the subjects' homes, including nausea and vomiting. The fecal sampling box comes with a pair of gloves and two sheets of toilet paper.

## **VIII 、 Data collection and statistical analysis**

Fecal samples of patients were sent to the company for metagenomic sequencing to obtain metagenomic data of microorganisms in the fecal samples.

The raw files obtained from the DNBSEQ-T7 platform were converted into short reads (raw data) via base call, and these short reads were recorded in FASTQ format [30] containing sequence information and corresponding sequencing quality information.

Sequence artifacts, including reads containing adapter contamination, low-quality nucleotides and unidentifiable nucleotides (N), undoubtedly set obstacles for subsequent reliable bioinformatics analysis. Therefore, quality control is a necessary step to ensure meaningful downstream analysis.

Fastp(version 0.23.1)[31] was used to perform basic statistics on the quality of the original reads.

The data processing steps are as follows:

- (1) Discard the paired reads if one of the reads contains adapter contamination;
- (2) Abandon paired reads if the number of uncertain bases exceeds 10% in each read;
- (3) Discard pairs of reads if the proportion of low-quality bases (Phred quality <5) in any read exceeds 50%.

After passing the quality inspection, a total of 0.2g of DNA is required for each sample as the input material for DNA library preparation. First, genomic DNA samples are ultrasonically crushed by a Covaris ultrasonic disruptor to meet a size requirement of 350bp. After terminal repair, adding A tail, adding sequencing headers, fragment screening, PCR amplification, and then using the AMPure XP system (Beverly, USA) to purify the product, the library quality was evaluated and quantified on the Agilent 5400 system (Agilent, USA), Quantification was performed using QPCR (1.5 nM). The 5' ends of each library were phosphorylated and cyclized. Then cyclic amplification is carried out to produce DNA nanospheres. Finally, the DNA nanospheres were loaded into flow cells for DNBSEQ-T7 sequencing at Novogene Bioinformatics Technology Co., LTD. (Beijing, China). The entire library preparation process is completed, resulting in the final DNA library.

Additionally, calculate the Bray-Curtis distance using the vegan package for principal coordinate analysis (PCoA). Linear discriminant analysis effect size (LEfSe) analysis was used for the Kruskal-Wallis test and the Wilcoxon rank sum test, and a  $p < 0.05$  was considered statistically significant. The LDA score was set to 2.0 to identify the characteristics with significant differences between groups. This study retained taxa with an average relative abundance greater than 0.0001(0.01%). The bar charts were visualized using the "ggplot2" package in R software (version 4.0.5)(<https://www.r-project.org/>).

All data were expressed as mean  $\pm$  standard error (SEM). The differences between groups were analyzed by one-way ANOVA using GraphPad Prism 7.0 software, and the results of the analysis were obtained by Tukey Test.

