# **I、 Research Background**

Colonoscopy is a must-have item in colorectal cancer check-ups, and for high-risk groups, annual check-ups are the most effective way of early prevention; A large amount of polyethylene glycol (PEG2000-4000) is used as a laxative and lubricant in colonoscopy at present; The extensive use of PEG can cause long-term and irreversible damage to the gut microbiota, posing a great threat to health.

The appendix, located at the base of the cecum, is a slender tubular structure that protrudes from the posterior wall inside the cecum and was once thought to be part of an evolutionary redundancy. Appendicitis has long been the most common surgical acute abdominal disease, and once acute appendicitis occurs, traditional treatments often opt for the removal of the appendix. In recent years, researchers have revealed that appendectomy is associated with mental disorders, colorectal cancer, cardiovascular diseases, etc. Besides being an important organ involved in immunity, the appendix also has the function of storing and protecting intestinal microbiota. When there is a disruption of the gut microbiota in the human body, the microorganisms retained in the appendix are released into the gut to reduce the impact of the disruption. Previous researchers' metagenomic sequencing of gut microbiota in patients who have undergone appendectomy shows significant changes in their gut microbiota compared to the normal population, which in turn affects central nervous system function through the microbiota-gut-brain axis and poses potential risks to host health and behavior, such as Parkinson's disease. Therefore, appendectomy may have potential adverse effects on the human body, such as significantly altering the composition of the gut microbiota, reducing the ability to restore intestinal homeostasis, and lowering the production of short-chain fatty acids (SCFAs).

This study will observe the effects of PEG on the gut microbiota, and by analyzing the changes in the gut microecology before and after colonoscopy, design better intestinal cleansing drugs and intestinal repair probiotics to further reduce the adverse effects of colonoscopy on patients. At the same time, explore the interaction between the appendix and the gut microbiota and its significance.

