## **2. Objectives of the study**

The study intends to recruit a group of people who have undergone appendectomy for colonoscopy, (1) to observe changes in gut microbiota before and after colonoscopy in the appendectomy population; (2) To analyze whether the changes in gut microbiota before and after colonoscopy in the appendectomy population were different from the recovery of the normal population.

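### Objective 2 asks whether the change after colonoscopy differs between groups, but no named analysis has a change score, a group-by-time term or a subject term, so an existing group difference can be read as different recovery

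*Protocol*

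**What the plan says.** Protocol, section 2 (Objectives of the study), gives as its second aim: "To analyze whether the changes in gut microbiota before and after colonoscopy in the appendectomy population were different from the recovery of the normal population". Section Iii (Study Design) repeats the comparison: "comparing the recovery and impairment of the microbiota with those who did not undergo appendectomy".

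Section VIII (Data collection and statistical analysis) names these methods:

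- At community level: "calculate the Bray-Curtis distance using the vegan package for principal coordinate analysis (PCoA"). No test on the distances is named.
- At taxon level, LEfSe: "analysis was used for the Kruskal-Wallis test and the Wilcoxon rank sum test", at p < 0.05 and an LDA score of 2.0, to find features that differ between groups.
- For the remaining data: "The differences between groups were analyzed by one-way ANOVA", followed by Tukey's test.

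The section does not define the groups, nor say whether the variable tested is a value at one visit or a change.

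Section I (Research Background) says that sequencing of patients after appendectomy "shows significant changes in their gut microbiota compared to the normal population". Section 5 says "About 10 people were included in this study", without a split between groups, an effect size, an SD or a power.

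**The concern.** Objective 2 is a group-by-time question. One-way ANOVA has a single factor, so it contains no interaction of group with time and no term for the person. The Kruskal-Wallis and Wilcoxon rank sum tests compare independent samples. PCoA is an ordination and tests nothing by itself. Applied to the measured abundances, these methods compare levels, not changes.

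That matters here because the protocol's own background predicts different levels before any bowel preparation. A between-group comparison after colonoscopy would carry that difference forward, and it could be reported as different recovery even if both groups changed in exactly the same way. Objective 2 is the only comparative objective of the two, so the main comparative conclusion is at risk.

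**Working it through.** **What each comparison estimates.** Let the control mean be μ before colonoscopy and μ + τ after it. Let the appendectomy mean be μ + δ before and μ + δ + τ + γ after. Here δ is the existing group difference, τ the change in controls and γ the difference in change.

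- Objective 2 asks about γ.
- The group contrast after colonoscopy is (μ + δ + τ + γ) − (μ + τ) = δ + γ.
- The group contrast in within-person change is (τ + γ) − τ = γ.

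The first contrast answers objective 2 only if δ = 0, and the Research Background expects δ ≠ 0.

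**Inputs.** From the protocol: about 10 people; significance at p < 0.05; one-way ANOVA with Tukey; Wilcoxon rank sum. The protocol gives no sample size derivation, so there is no figure to reproduce first. Assumed, because the protocol does not state them: 5 per group (or 10 per group, if the 10 is read that way); 2 or 4 visits; within-person correlation ρ of 0.5 to 0.8; δ = 1 or 1.5 SD; a common change τ = 0.5 SD; γ = 0; normal data.

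**Tests, applied by simulation.**

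- Tukey over the k group-by-visit cells: significant if |difference in means| / √(MSE/n) exceeds the 95% point of the studentized range with k cells and k(n − 1) degrees of freedom. For n = 5 this is k = 4 and 16 df with 2 visits, and k = 8 and 32 df with 4 visits.
- Wilcoxon rank sum between groups on the post-colonoscopy values.
- Two-sample t-test on within-person change, which with two visits is the group-by-time interaction.

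**Share of trials significant when the true difference in change is zero.**

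| Setting | Test | δ = 1 SD | δ = 1.5 SD |
|---|---|---|---|
| 5 per group, 2 visits | Tukey, post-colonoscopy | 14–17% | 36% |
| 5 per group, 4 visits | Tukey, post-colonoscopy | 7–9% | 23–25% |
| 5 per group | Wilcoxon, post-colonoscopy | 21% | 43% |
| 10 per group, 2 visits | Tukey, post-colonoscopy | 34% | 74% |
| 10 per group | Wilcoxon, post-colonoscopy | 51% | 86% |
| Either size | Test of change | 5% | 5% |

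All entries are approximate. With δ = 0 and 2 visits, the Tukey contrast is significant in about 1% of trials and Wilcoxon in about 3–5%, so the excess comes from the existing difference.

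**What a test of change could detect.** At 80% power and two-sided 5%, the two-sample t-test detects about 2.0 SD of the change with 5 per group and about 1.3 SD with 10 per group. The SD of a change is √(2(1 − ρ)) times the SD of a single measurement: 1.0 at ρ = 0.5 and 0.63 at ρ = 0.8. So 2.0 SD of the change is about 2.0 or 1.3 measurement SDs respectively.

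**The case against.** The strongest defence is that the analysis section never defines its groups or its variable. ANOVA or rank tests applied to change scores would answer objective 2. The statistical text also begins abruptly after the library preparation, the study flow figure is not shown, and reference numbers in the text run beyond the reference list, so some text may be missing. This stands to the extent that one cannot say the plan is only able to compare levels. But the text available names no change score or paired quantity, and describes both LEfSe and the ANOVA as comparisons between groups.

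A second defence is that a Tukey table over group-by-visit cells would also show the contrast before colonoscopy, so an existing difference need not be hidden. That is fair, but seeing two contrasts side by side is not a test of their difference.

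A third is that the percentages rest on assumptions. They do. Their size moves with δ, the number of visits and the group size; the direction does not.

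Two stronger readings are tempting and should not be made. A reader might infer that the trial will call recovery different when one group's before/after test is significant and the other's is not. The protocol does not say so, and the size of that risk depends on the change assumed: with Tukey, 2 visits and 5 per group, exactly one group is significant in about 24–34% of trials at a common change of 1.5 SD, but in only about 0.5–2% at 0.5 SD. A reader might also infer that recovery will be declared from a non-significant result. Nothing in the document says this either.

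**Conclusion.** Wrong as written. The protocol commits itself to named methods, so this is a mismatch between an objective and its stated analyses rather than a detail left to a statistical analysis plan. As described, those methods contain no within-person change, no group-by-time term and no subject term, while the protocol itself expects the groups to differ beforehand.

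Under the assumptions listed, with 5 per group and no true difference in change, a post-colonoscopy group test by the named methods is significant in roughly 7% to 43% of trials, depending on test, visits and existing difference. A test of change gives about 5%. Higher rates come from 10 per group, where more people make the existing difference easier to detect. The algebra behind the conclusion needs none of these assumptions; only the percentages do. The conclusion would fall away if the investigators intended the tests to act on change from baseline, in which case the protocol needs to say so.

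**What to change.** Add to section VIII, for objective 2:

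- **Taxa and other single-number measures.** Compare the within-person change from the pre-colonoscopy sample between groups, by a two-sample or permutation test on the change, or equivalently by a group-by-visit term in a model with subject as a random effect. Name the post-colonoscopy visit or visits used. Report the estimated difference with its 95% CI. With 5 against 5, an exact permutation test can reach a two-sided p of 2/252 = 0.008, so it is usable at this size.
- **Community level.** Compute each person's Bray-Curtis distance to their own pre-colonoscopy sample and compare it between groups by permutation. State that this measures the size of the shift and not its direction, and that ordinary variation between samples from one person also enlarges it.
- **Descriptive only for this objective:** the PCoA and group contrasts at post-colonoscopy visits.

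The comparison needs samples before and after colonoscopy from controls as well. In section 4, the inclusion criteria for controls do not list colonoscopy, while the exclusion criteria describe the controls as the colonoscopy population without appendectomy. These statements must be reconciled.

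If controls are sampled at both times, as objective 2 presupposes, the cost is a few sentences and slightly more analysis work. If they are not, sampling has to change. The fix prevents a false conclusion but does not supply power: with about 10 people, only large differences in change are detectable.

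### The LEfSe rule calls taxa significant at p < 0.05 with LDA 2.0 and names no control for the number of taxa tested, so chance findings are expected

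*Protocol*

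**What the plan says.** Section VIII of the protocol (Data collection and statistical analysis) fixes the rule for taxa in three steps.

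- The test: "Linear discriminant analysis effect size (LEfSe) analysis was used for the Kruskal-Wallis test and the Wilcoxon rank sum test".
- The threshold: a p-value below 0.05 "was considered statistically significant". No adjusted p-value, q-value or false discovery rate is mentioned.
- The effect-size filter: "The LDA score was set to 2.0 to identify the characteristics with significant differences between groups".

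The same section keeps taxa whose mean relative abundance exceeds 0.01%, without saying how many that leaves. The only multiple-comparison method in the document belongs to the separate one-way ANOVA, where "the results of the analysis were obtained by Tukey Test".

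The sample-size section reads in full: "About 10 people were included in this study". It does not say whether this is the total or the number per group.

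On the use of the results, the Study Design section says that recovery and impairment are compared "to design corresponding microecological restoration probiotics". The Research Background gives the aim to "design better intestinal cleansing drugs and intestinal repair probiotics".

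**The concern.** A threshold of 0.05 limits the error of one test. Shotgun metagenomic data give many taxa, and a rule that judges each at 0.05 yields a number of false declarations that grows in proportion to the number tested. The Tukey step does not help, because it adjusts for pairs of groups within one variable and not for the number of taxa.

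The LDA cut-off can look like a second safeguard. It is not one: the score comes from the same samples as the p-value. In small groups, a chance difference large enough to reach p < 0.05 is usually large enough to pass the score as well.

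At stake is how the results are read. A study in which neither appendectomy nor bowel preparation changed any taxon would still be expected to report a list of significant ones, and nothing in the section marks that list as exploratory.

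**Working it through.** The protocol gives no error rate, power or taxon count, so there is no figure to reproduce. The check asks how many taxa the stated rule passes when no taxon truly differs.

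**Inputs.** From section VIII: rank tests, p < 0.05, LDA 2.0. From the sample-size section: about 10 people, read either as 5 v 5 (total) or as 10 v 10 (per group); equal groups are an assumption. Number of taxa m: not in the document, assumed 50 to 500.

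**Size of one test at 5 v 5.** There are C(10,5) = 252 equally likely rank allocations. The rank sum W of one group has mean 27.5 and variance 5 × 5 × 11/12 = 22.92.

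- Exact Wilcoxon: p < 0.05 needs W ≤ 17 or its mirror image. W = 15, 16, 17 arise in 1, 1 and 2 ways, so the size is 2 × 4/252 = 8/252 = 3.2%.
- Kruskal-Wallis with the chi-square approximation: W = 18 gives H = 9.5²/22.92 = 3.94, above 3.84, and arises in 3 ways. The size is 2 × 7/252 = 14/252 = 5.6%.
- Smallest possible exact two-sided p: 2/252 = 0.0079.

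**Size at 10 v 10.** Full enumeration gives 4.3% (exact) and 5.2% (chi-square), with a smallest exact p of 0.000011.

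**Expected false positives** = m × size:

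| Assumed null taxa m | 5 v 5, exact | 5 v 5, chi-square | 10 v 10, exact | 10 v 10, chi-square |
|---|---|---|---|---|
| 50 | 1.6 | 2.8 | 2.2 | 2.6 |
| 100 | 3.2 | 5.6 | 4.3 | 5.2 |
| 300 | 9.5 | 16.7 | 13.0 | 15.7 |
| 500 | 15.9 | 27.8 | 21.6 | 26.2 |

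With two groups, both tests rank the same data, so the exact column also covers a rule that requires both to be passed.

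**Chance of at least one**, if taxa were independent, is 1 − (1 − size)^m. At 5 v 5 this is 80–94% for 50 taxa and 96.0–99.7% for 100. Correlation between taxa lowers this chance but leaves the expected numbers in the table unchanged.

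**Effect of the LDA cut-off.** A null simulation used log-normal abundances, the 0.01% filter, 300 runs per setting and an approximate score: log10 of 1 plus half the mean difference per million. Mean false positives before and after the cut-off of 2.0 were:

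| Taxa simulated (mean retained at 5 v 5) | 5 v 5 | 10 v 10 |
|---|---|---|
| 50 (47.7) | 2.55 → 2.52 | 2.38 → 2.30 |
| 100 (90.3) | 4.91 → 4.78 | 4.84 → 4.50 |
| 200 (164.2) | 8.68 → 8.17 | 8.77 → 7.76 |
| 500 (336.2) | 18.85 → 17.17 | 17.90 → 14.74 |

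The largest reduction is 1 − 14.74/17.90 = 18%; at 5 v 5 it is at most 1 − 17.17/18.85 = 9%.

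**What adjustment would leave.** Benjamini-Hochberg at 5% can declare k taxa at the smallest p only if k ≥ p_min × m/0.05. At 5 v 5 with exact p-values this needs 8, 16, 48 and 80 taxa for m = 50, 100, 300 and 500 (for example 0.0079 × 300/0.05 = 47.6, so 48). At 10 v 10 one taxon at the smallest exact p suffices for every m in the range.

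**The case against.** The strongest reply is that handling of multiplicity in a sequencing screen is often left to the statistical analysis plan, which is not at hand and may add a false discovery rate step. The protocol also never calls its p-values unadjusted. Part of this stands: a later plan could cure the problem. But the protocol does more than stay silent. It states the threshold, calls results beyond it significant and names no adjustment, so an analyst who follows it as written gets the numbers above.

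A second reply is that the aims are to observe and compare microbiota, with no primary endpoint or treatment decision tied to the taxon list. That is fair, and it limits how serious the point is.

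Some stronger readings are tempting but not supported.

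- A reader might infer that the LEfSe list is the declared basis for choosing probiotics. No sentence says so. The Background and Study Design sections state the probiotic aim, and LEfSe is the only taxon-selection method named; the link between them is inference.
- A reader might multiply the counts by the number of visits and taxonomic levels. The readable text names neither, and the technical route is a figure that is not shown.
- A reader might take 5 v 5 as given. It is one reading of the sample-size sentence. Under 10 v 10, the floor on the p-value is no longer an obstacle.
- The sentence on the abundance filter does not say outright that it sets the list of taxa tested. Treating it so is reasonable, but this is another reason to show a range for m.

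**Conclusion.** The point holds. As written, the rule is expected to declare about 3–6% of truly unaffected taxa significant: 3.2–5.6% at 5 v 5 and 4.3–5.2% at 10 v 10. In the simulation, the LDA cut-off removed only a small part of these. The conclusion does not turn on which reading of the sample size is right, on the form of the p-value, or on any taxon count between 50 and 500. The counts themselves do depend on the assumed m and on equal groups. The LDA result also depends on the approximate score and the assumed abundance distribution.

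This should be fixed before analysis, but it does not undermine the study. The aims are largely descriptive, and the route from a false taxon to a probiotic is a possibility that the document leaves open, not a step that it prescribes.

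**What to change.** In section VIII, state that Benjamini-Hochberg adjustment is applied to the planned rank-test p-values across all retained taxa at one taxonomic level named in advance, before any LDA filtering. Report adjusted and unadjusted p-values side by side, call a taxon significant only on the adjusted value, and present LDA scores as descriptive. Label any taxa listed on unadjusted p-values as hypothesis-generating, needing confirmation in independent samples before they inform probiotic design.

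The cost is a few sentences and one added step in the analysis code. It needs no new data and no change of model; the planned rank tests can stay. The downside is that fewer taxa will be declared. If the total is 10, split 5 v 5, perhaps none will be, because the exact p-value cannot fall below 0.0079. The label is therefore needed as well as the adjustment: with groups that small, adjustment alone would leave the unadjusted list as the only one with content. The sample-size section should also say whether its figure is the total or per group, since that decides whether adjusted significance is realistically attainable.
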